16.2.2. LIVER FUNCTION RELATED CRITERIA

Liver function-related laboratory tests will be summarized in accordance to the criteria in Table F.

Table F: Liver Function Pre-defined Criteria

| Liver Function Parameter | Criteria |
|--------------------------|-----------|
| ALT | ≥ 3 x ULN |
| | ≥ 5 x ULN |
| AST | ≥ 3 x ULN |
| | ≥ 5 x ULN |
| GGT | ≥ 3 x ULN |
| | ≥ 5 x ULN |

Document: Author: ...\ITI\ITI-007\MYA11638\Biostatistics\Documentation\SAP\ITI-007-404 SAP Final V1.0 12JUN2019.docx

Version Number:1.0

Version Date:

Page 36 of 53

| Total Bilirubin | > 1.5 X ULN |
|---|-------------|
| (in combination with ALT or AST criteria) | > 2 x ULN |
| СРК | ≥ 5 x ULN |
| Hy's Law | Criteria |
| ALT or AST | ≥ 3 x ULN |
| Total Bilirubin | > 2 X ULN |
| Alkaline phosphatase | < 2 x ULN |

16.3. **ECG EVALUATIONS**

ECG will be performed during screening, at baseline, Day 43 or Early Termination Visit and on the Day 57 safety follow-up for all subjects. At screening ECGs will be collected in triplicate and will be analyzed as an average of the non-missing measurements at each time point. In all cases, ECGs are conducted before other assessments scheduled in the same time window. Results from the central ECG (Electrocardiogram) Reading Centre will be included in the reporting of this study.

The following ECG parameters will be reported:

- HR (bpm)
- QRS Interval (msec)
- PR Interval (msec)
- QT Interval (msec)
- QTcF Interval (msec) [derived by central ECG]
- QTcB Interval (msec) [derived by central ECG]
- RR Interval (msec)
- Overall assessment of ECG

For the overall ECG assessment, there are five possible results for each triplicate: 'Abnormal, Significant', 'Abnormal Insignificant', 'Incomplete Analysis', 'Normal', and 'Uninterpretable'. Overall assessments with a result of 'Incomplete Analysis' or 'Uninterpretable' will be considered missing. Triplicates will be analyzed according to the worst assessment and categorized in the following order, 'Abnormal Significant', 'Abnormal, Insignificant' and 'Normal'.

The following summaries will be provided for ECG data:

- Actual and change from baseline by visit (for quantitative measurements, except unadjusted QT)
- Incidence of abnormal and normal ECGs by visit

...\ITI\ITI-007\MYA11638\Biostatistics\Documentation\SAP\ITI-007-404 SAP Final V1.0 12JUN2019.docx Document: Author: Version Number: 1.0

Page 37 of 53

- Shift from baseline to each visit according to markedly abnormal criteria (for quantitative measurements and categorical measurements)
- Incidence of markedly abnormal results defined in Section 16.3.1
- Listing of subjects meeting markedly abnormal criteria

16.3.1. ECG MARKEDLY ABNORMAL CRITERIA

Markedly abnormal quantitative ECG measurements will be identified in accordance with the following predefined markedly abnormal criteria:

- Absolute values for QT, QTcB and QTcF intervals will be classified as:
- > 450 msec
- o > 480 msec
- o > 500 msec
- o Change from Baseline for QT, QTcB and QTcF intervals will be classified as:
- > 30 msec increase from baseline
- > 60 msec increase from baseline

16.4. VITAL SIGNS

The following vital signs measurements will be reported for this study:

- Systolic blood pressure (mmHg)
- Diastolic blood pressure (mmHg)
- Pulse rate (bpm)
- Respiratory rate (breaths/min)
- Oral temperature (⁰C)
- Height (cm) at screening
- Weight (kg)
- BMI (kg/m²) [calculated as weight (kg) / height (m)²]

Vital signs, including systolic blood pressure, diastolic blood pressure, pulse rate, respiratory rate, oral temperature and body weight, are recorded at screening, baseline and Days 8, 15, 22, 29, 36, 43 and 57At screening, baseline and days 43 and 57 vital signs include the 3-positional blood pressure and pulse rate will be measured after 10 minutes in the supine position, 1-minute sitting, immediately after standing, and 3 minutes after standing at screening, baseline, day 43 and day 57. These 3-positional results will be averaged at each visit and used for the summary and analyses. Pulse will be measured by counting pulse over 60 seconds. Height will be measured only at screening.

BMI measurements classify a subject's weight status as underweight, normal, overweight, or obese using Table G:. Shifts from Baseline to Day 43 will be produced by treatment group for the SAF Set to show the percentage of subjects who fall into each BMI category combination.

Document: ...\ITI\ITI-007\MYA11638\Biostatistics\Documentation\SAP\ITI-007-404 SAP Final V1.0 12JUN2019.docx Author: Version Number:1.0

Page 38 of 53

Table G: **BMI Weight Status Categories**

| BMI (kg/m²) | Weight Status |
|-------------------|---------------|
| < 18.5 | Underweight |
| 18.5 ≤ BMI < 25.0 | Normal |
| 25.0 ≤ BMI < 30 | Overweight |
| 30.0 ≤ BMI | Obese |

The following summaries will be provided for vital sign data:

- Actual and change from baseline by visit
- Incidence of markedly abnormal values
- Listing of subjects meeting markedly abnormal criteria
- Shifts from baseline by visit and time point according to markedly abnormal criteria.
- BMI shift summaries

The analysis of change from baseline in all vital sign measurements to Day 43 will be performed using an MMRM method. The model will include visit. Bipolar Disorder stratification variable at screening (Bipolar I or Bipolar II), site (or pooled site) and treatment as factors, baseline values as covariate and interaction terms for baseline baseline value-by-study visit. The subject term will be included in the model as a random effect while all other terms will be considered fixed effects. Summary statistics for change from baseline will be presented by treatment group and study visit (Day) as well as LSM estimates and the the associated standard error.LSM differences between 60mg ITI-007 and placebo, the associated standard errors, 95% CIs and p-values for between-treatment tests of differences will be presented for each study visit (Day).

As an exploratory analysis, change from baseline in these vital signs to each assessment time point will also be evaluated using an ANCOVA with LOCF model with effects for study visit. baseline value, Bipolar Disorder stratification variable at screening (Bipolar I or Bipolar II), site (or pooled site) and treatment. LSMs and the associated standard errors for each treatment group (ITI-007 60 mg or placebo), the LSM differences for between-treatment comparisons (ITI-007 60 mg vs. placebo), the corresponding standard errors, 95% CIs and p-values for the between-treatment differences will be presented for each assessment time point.

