| | | ≥40 days relative to Day 1 date and after the last dose of treatment and before the start of the Safety Follow-up Period (one day after actual Day 43 visit) | Day 43 | 6 |
| Post-treatment | Safety Follow-up | > 43 days relative to Study Day 1 date for treatment completers (42 days on-treatment) and after Day 43 post-treatment assessments. | Day 57 | 8 |

^{*} Not to exceed maximum allowed days

Baseline assessments are scheduled for Visit 2 on Relative Study Day 1, prior to first treatment of study medication. Unless otherwise specified, baseline is defined as the last non-missing measurement before the first dose of study medication.

Assessments will be considered baseline if the date of the last pre-treatment measurement is before the date of the first treatment or if the measurement was done on Study Day 1 and, according to the Study Schedule of Events, was supposed to be performed on Day 1, prior to treatment (including unscheduled measurements).

For parameters planned to be collected multiple times at the same time point (3-positional

Document: ...\ITI\ITI-007\MYA11638\Biostatistics\Documentation\SAP\ITI-007-404 SAP Final V1.0 12JUN2019.docx Author: Version Number:1.0

Version Date: 12

Page 15 of 53

blood pressure), the average of the last non-missing pre-treatment measurements will be considered as baseline.

Unless otherwise specified, the following calculations will be used for change from baseline and percent change from baseline:

Change from baseline visit will be calculated as:

Value at Visit X – Baseline Value

Percent change from baseline will be calculated as:

• Value at Visit X – Baseline Value

Baseline Value × 100

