8. OUTPUT PRESENTATIONS

The Tables, Listings and Figures (TLFs) shells provided with this SAP describe the presentations for this study and therefore the format and content of the summary TLFs to be provided by IQVIA Biostatistics.

Continuous variables will be summarized using descriptive statistics (number of subjects [n], mean, standard deviation [SD], median, minimum, and maximum, unless otherwise stated). The minimum and maximum will be reported to the same number of decimal places as the raw data recorded in the database. The mean and median will be reported to one more decimal place than the raw data recorded in the database. The SD will be reported to two more decimal places than the raw data recorded in the database.

Categorical variables will be summarized using frequency counts and percentages. Unless otherwise stated, the calculation of percentage will be based on the number of subjects in the analysis set of interest.

P-values will be presented to three decimal places. P-values less than 0.001 will be presented as "<0.001".

Confidence intervals (CIs) will be presented to two more decimal places than the raw data.

Source data for summary tables and statistical analyses will be presented as subject data listings.

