16.4.1. VITAL SIGNS MARKEDLY ABNORMAL CRITERIA

Markedly abnormal quantitative vital signs measurements will be identified in accordance with the following predefined markedly abnormal criteria in the table below.

...\ITI\ITI-007\MYA11638\Biostatistics\Documentation\SAP\ITI-007-404 SAP Final V1.0 12JUN2019.docx Document: Author:

Page 39 of 53

Table H: Markedly Abnormal Criteria for Vital Signs

| Variable | Unit | Low | High |
|------------|------|--|---|
| SBP | mmHg | < 90 mmHg AND | > 180 mmHg AND |
| | | decrease from baseline ≥ 20 mmHg | increase from baseline ≥ 20 mmHg |
| DBP | mmHg | < 50 mmHg AND | > 105 mmHg AND |
| | | decrease from baseline | increase from baseline ≥ 15 |
| | | ≥ 15 mmHg | mmHg |
| Pulse rate | bpm | < 50 bpm AND | > 120 bpm AND |
| | | decrease from baseline ≥ 15 bpm | increase from baseline ≥ 15 bpm |
| Weight | Kg | percentage change from baseline ≤ -7.0 % | percentage change from baseline ≥ 7.0 % |

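### Averaging supine, sitting and standing readings dilutes a standing-only change and hides that it is postural, although the protocol lists such an effect as observed

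*SAP*

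**What the plan says.** Protocol 8.1.5 schedules positional blood pressure at V1, V2, V8 and V9 only (screening, baseline, Day 43, Day 57). Each set has four readings in three positions: supine, sitting, immediately on standing, and about 3 minutes after standing. SAP 16.4 repeats this schedule and includes pulse.

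SAP 16.4 then collapses the set: "These 3-positional results will be averaged at each visit and used for the summary and analyses". For positional blood pressure, SAP 7 does the same at baseline: "the average of the last non-missing pre-treatment measurements will be considered as baseline".

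The rest of the vital-sign plan follows from that single value:

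- **Model.** "The analysis of change from baseline in all vital sign measurements to Day 43 will be performed using an MMRM method". Neither this model nor the exploratory ANCOVA with LOCF has a term for position.
- **Table H (SAP 16.4.1).** The low systolic flag needs a value below 90 mmHg together with a "decrease from baseline ≥ 20 mmHg". The low diastolic flag needs a value below 50 mmHg and a fall of at least 15 mmHg. Both compare a visit with baseline; neither compares standing with supine.
- **Shift tables.** SAP 16.4 lists "Shifts from baseline by visit and time point according to markedly abnormal criteria". The matching ECG item in SAP 16.3 reads "Shift from baseline to each visit according to markedly abnormal criteria", with no mention of time point.

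**The concern.** Averaging suits repeated measurements of one quantity. Supine and standing pressure are different quantities, and the contrast between them is what a positional set is taken to show. Once averaged, a fall confined to standing shrinks and cannot be told apart from a smaller fall in all positions.

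This matters here because protocol 2.3.1 includes a drop in blood pressure or a rapid pulse on rising among the effects seen with ITI-007. Day 43 is the only post-baseline positional visit at the end of treatment; protocol section 4 places the follow-up visit about 2 weeks after the last dose. If the Day 43 readings are averaged, the planned tables have no other scheduled visit that could show an on-treatment postural difference between the arms.

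**Working it through.** The documents give no figure of their own on this point, so there is none to reproduce. The check is arithmetic on the averaging rule. All blood pressure values below are assumed, for illustration.

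**Weights.** The SAP does not say how four readings in three positions are averaged, so both natural readings were tried:

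- (a) four readings weighted equally;
- (b) three positions weighted equally, with the two standing readings averaged first.

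With supine and sitting unchanged, change in the average = weight × standing change.

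| Standing readings that change | Weight (a) | Weight (b) | A 30 mmHg fall becomes |
|---|---|---|---|
| Both | 2/4 = 1/2 | 1/3 | 15 or 10 mmHg |
| Immediate only | 1/4 | 1/3 × 1/2 = 1/6 | 7.5 or 5 mmHg |

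**Table H, systolic.**

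- Fall component: for the average to fall 20 mmHg, both standing readings must fall 20 ÷ 1/2 = 40 mmHg under (a) or 20 ÷ 1/3 = 60 mmHg under (b).
- Absolute component: with supine and sitting at 120, the average is below 90 only if both standing readings are below (4×90 − 2×120)/2 = 60 under (a), or 3×90 − 2×120 = 30 under (b).

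**Systolic example** (supine / sitting / immediate standing / 3-minute standing): baseline 124/122/120/121, Day 43 124/122/86/92.

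- (a) 487/4 = 121.75 to 424/4 = 106.0: change −15.75.
- (b) (124+122+120.5)/3 = 122.17 to (124+122+89)/3 = 111.67: change −10.5.
- Neither average meets Table H.
- Immediate standing alone: 120 to 86, a fall of 34 and below 90, so Table H is met.
- Supine to immediate standing: 120 − 124 = −4 at baseline, 86 − 124 = −38 at Day 43.

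**Diastolic example:** baseline 78/80/80/80, Day 43 78/80/46/56.

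- (a) 318/4 = 79.5 to 260/4 = 65.0: change −14.5.
- (b) (78+80+80)/3 = 79.33 to (78+80+51)/3 = 69.67: change −9.67.
- Neither average meets Table H.
- Immediate standing alone: 80 to 46, a fall of 34 and below 50, so Table H is met.

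**Identifiability.** Under (a), a patient whose four systolic readings each fell 15.75 mmHg has the same average change as the patient in the systolic example, with no postural change at all.

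**Limit of the effect.** A fall of the same size in every position is not diluted. The problem is specific to changes that differ by position.

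**The case against.** Several points on the other side are fair.

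- **The risk basis is modest.** Protocol 2.3.1 gives no rate or placebo comparison for the postural effect, and protocol 2.2 describes 60 mg as having a safety profile similar to placebo. The safety objective is change in vital signs, with no orthostatic endpoint, and efficacy is untouched. This limits the weight of the point.
- **The readings are not lost.** SAP 8 says: "Source data for summary tables and statistical analyses will be presented as subject data listings". Symptomatic events, and readings the investigator judges clinically significant, can be reported as adverse events (protocol 8.1.5 and 8.5.1). The patient in the example might well be reported that way. Protocol 10.1 adds blinded review of outlying safety values. But listings and blinded review are not comparisons between arms, and an asymptomatic standing fall not judged significant would reach the by-arm vital-sign results only in diluted form.
- **The shift tables or unseen shells may be by position.** SAP 8 assigns "the format and content of the summary TLFs" to shells that are not available, and *time point* in the shift item could be meant as position. SAP 7 points the other way: it treats the positional blood pressure readings as several measurements at one time point. A by-position shell would also conflict with the averaging sentence and would need reconciling.
- **The protocol allows averaging.** Protocol 12.4.4 averages parameters collected in duplicate or triplicate. Readings in different positions are not replicates, so that rule does not cover them.
- **The 40 and 60 mmHg figures cover only half of the Table H criterion.** That is correct. The working therefore shows the absolute limit as well, and in its example that limit is harder still to reach.

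**Conclusion.** The concern holds. Followed as written, SAP 16.4 and SAP 7 reduce a standing-only change to between 1/2 and 1/6 of its size, depending on the weighting and on whether one or both standing readings change, and they remove the means of recognizing it as postural. No visible summary, model or flag restores it.

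The dilution rests only on supine and sitting readings being unchanged and is certain under either weighting. The patient examples use assumed values and say nothing about how often such falls occur. Confidence is lower for the Table H shift tables, because of the *time point* wording and the unseen shells. The defect lies in a planned safety analysis, does not affect the primary endpoint, and should be corrected because the correction is cheap.

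**What to change.** Replace the averaging sentence in SAP 16.4 and the positional-average baseline in SAP 7 with the following.

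1. Summarize blood pressure by position, each against its same-position baseline, at Day 43 and Day 57.
2. Apply the existing Table H criteria to each position, and state whether *time point* in the shift item means position.
3. Add by-arm summaries of supine-to-standing change in systolic and diastolic pressure at baseline, Day 43 and Day 57. Make Day 43 the on-treatment comparison: a single-visit comparison adjusted for the baseline value, not an MMRM. State how patients without a Day 43 positional set are handled, since protocol 8.1.5 does not name the early discontinuation visit as positional.
4. Keep the planned MMRM over Days 8–43 and the exploratory ANCOVA with LOCF, but feed them one stated position at every visit, including baseline, matching the position used at Days 8–36 where it was recorded. If it was not recorded, name the position used for baseline and Day 43 and state the possible mismatch. The model text in SAP 16.4 also lists no treatment-by-visit term although it reports differences at each visit; that is a separate matter, and items 1–3 do not depend on it.
5. Reconcile protocol 8.1.5, which makes only blood pressure positional, with SAP 16.4, which includes pulse. If pulse is taken by position, treat it in the same way.

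The cost is more rows in the safety tables and one sentence in the model specification. Blood pressure by position is already scheduled, so no new blood pressure measurement is needed, and no new threshold is introduced.

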15.1.3. PRIMARY ANALYSIS OF PRIMARY EFFICACY VARIABLE

The treatment effect on the primary efficacy endpoint will be estimated using an MMRM method. The model will include the change from baseline at each pre-specified time point as the response variable, study visit, Bipolar Disorder stratification variable at screening (Bipolar I

Document: ...\ITI\ITI-007\MYA11638\Biostatistics\Documentation\SAP\ITI-007-404 SAP Final V1.0 12JUN2019.docx
Author: Version Number:1.0

Version Number 1.0

Page 24 of 53

or Bipolar II), treatment (60 mg ITI-007 or placebo) and site (or pooled site) as factors, baseline MADRS total score as covariate and interaction terms for baseline MADRS total score-by-study visit and treatment-by-study visit. The subject term will be included in the model as a random effect while all other terms will be considered fixed effects. An unstructured covariance matrix will be used to model the correlation among repeated measurements within subject.

The Kenward-Rogers method will be used to estimate the denominator degrees of freedom. The treatment and treatment-by-study visit interaction terms allow for comparisons of the treatment groups at the time point of interest (Days 8, 15, 22, 29, 36 and 43). Treatment differences will be evaluated via contrasts for the study visit-by-treatment factor.

The change from baseline to Day 43 will be used for the primary efficacy analysis, and will be performed for the ITT Set

Summary statistics for change from baseline in MADRS total score will be presented by treatment group and study visit (Day), as well as least-squares mean (LSM) estimates. standard errorsand the corresponding 95% CI for LSMs.Contrast estimates (LSM differences) for between-group comparison, the corresponding standard errors, 95% CIs, effect sizes, and p-values will also be presented for each study visit (Day). Effect size will be calculated for the ITI-007 60 mg treatment group as:

LS Mean Difference

Pooled estimate of within subject error standard deviation

15.2. **KEY SECONDARY EFFICACY ENDPOINT**

The key secondary efficacy endpoint is the change from baseline to Day 43 in the Clinical Global Impression scale, Bipolar Version, for Severity (CGI-BP-S).

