The CGI-BP-S is a single value assessment of illness severity in mania, depression and overall bipolar illness and ranges from 1='Normal, not at all ill' to 7='Very severely ill' It is used in this study at screening (as a criterion for inclusion or exclusion), at baseline, and throughout the study, at Days 8, 15, 22, 29, 36, and 43. A higher score is associated with greater illness severity. The CGI-BP-S has 3 subscales, one each for mania, depression and overall bipolar illness. These 3 subscales are included in the calculation of the CGI-BP-S total score which will be recorded on the Clinical Global Impressions – Bipolar (CGI-S-BP) CRF page.

...\ITI\ITI-007\MYA11638\Biostatistics\Documentation\SAP\ITI-007-404 SAP Final V1.0 12JUN2019.docx Document: Author:

[figure not shown]
Version Number:1.0

Page 25 of 53

Change from baseline in the CGI-BP-S total score will be evaluated using an MMRM method similar to the one specified for the primary analysis of the primary efficacy endpoint, where the change from baseline to each pre-specified time point in CGI-BP-S total score is the response variable, study visit, Bipolar Disorder stratification variable at screening (Bipolar I or Bipolar II), treatment (60 mg ITI-007 or placebo) and site (or pooled site) as factors, baseline CGI-BP-S total score as covariate and interaction terms for baseline CGI-BP-S total score-by-study visit and treatment-by-study visit. The subject term will be included in the model as a random effect while all other terms will be considered as fixed effects. See Section 15.1.3, the primary analysis of primary efficacy endpoint, for more details.

Document:

...\ITI\ITI-007\MYA11638\Biostatistics\Documentation\SAP\ITI-007-404 SAP Final V1.0 12JUN2019.docx

Author:

Version Number: 1.0

Page 26 of 53

Document:

...\ITI\ITI-007\MYA11638\Biostatistics\Documentation\SAP\ITI-007-404 SAP Final V1.0 12JUN2019.docx

Author:

Version Number:1.0

Version Date: 12JUN2

STATISTICAL ANALYSIS PLAN: PROTOCOL ITI-007-404
Page 27 of 53

Document: Author: ...\ITI\ITI-007\MYA11638\Biostatistics\Documentation\SAP\ITI-007-404 SAP Final V1.0 12JUN2019.docx

or: Version Number:1.0

Version Date: 12JUN2019

Document:

...\ITI\ITI-007\MYA11638\Biostatistics\Documentation\SAP\ITI-007-404 SAP Final V1.0 12JUN2019.docx

Author:

Version Number:1.0

Version Date: 12JUN2019

[figure not shown]

Document: Author: ...\ITI\ITI-007\MYA11638\Biostatistics\Documentation\SAP\ITI-007-404 SAP Final V1.0 12JUN2019.docx

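### SAP 16.4 promises vital-sign differences at every visit and at Day 43, but its MMRM names no treatment-by-visit term and can give only one common difference.

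*SAP*

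**What the plan says.** SAP section 16.4 sets the target: "The analysis of change from baseline in all vital sign measurements to Day 43 will be performed using an MMRM method". The factors are visit, bipolar stratum, site and treatment. The clause that ends the list reads "treatment as factors, baseline values as covariate and interaction terms for baseline baseline value-by-study visit", so baseline-by-visit is the only interaction named. On dependence within subjects it says only "The subject term will be included in the model as a random effect while all other terms will be considered fixed effects". The promised output is visit-specific: LSM differences, standard errors, confidence intervals and "p-values for between-treatment tests of differences will be presented for each study visit (Day").

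The two efficacy models are specified differently. Section 15.1.3 includes treatment-by-visit and gives the reason: "The treatment and treatment-by-study visit interaction terms allow for comparisons of the treatment groups at the time point of interest". Section 15.2 lists "interaction terms for baseline CGI-BP-S total score-by-study visit and treatment-by-study visit" and then sends the reader to 15.1.3 for further detail. Section 16.4 has no such cross-reference.

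Section 16.4 adds an exploratory analysis: "change from baseline in these vital signs to each assessment time point will also be evaluated using an ANCOVA with LOCF model". Its listed effects include study visit.

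**The concern.** A model with treatment as a main effect only assumes the same treatment difference at Day 8, Day 43 and every visit between. A table built from it would print one estimate, one interval and one p-value six times under six visit labels. The Day 43 row would answer the stated Day 43 question only if the effect were constant over time, and neither document claims that.

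For blood pressure and pulse there is a further reason for doubt. Protocol 8.1.5 and SAP 16.4 schedule the multi-position readings at screening, baseline, Day 43 and Day 57, and the SAP averages them at each visit. The visits from Day 8 to Day 36 have no such set. Protocol 2.3.1 lists low blood pressure or fast heartbeat on standing among observed effects, so position may matter. A common difference would pool Day 43 with visits measured differently.

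A programmer who follows 16.4 literally gets the wrong contrast. One who adds the missing term departs from the written plan.

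**Working it through.** The plan gives no figure to reproduce here. The check is algebra, followed by an illustration whose trajectories, correlations and dropout rates are assumptions.

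**Inputs from the documents.** There are six post-baseline visits up to Day 43: Days 8, 15, 22, 29, 36 and 43 (SAP 16.4). The model terms are those set out above.

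**The contrast.** Let T be treatment (0 or 1) and B the baseline value. Within a stratum and site, the model as written has mean at visit j

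m_j + τT + β_jB.

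The treatment difference at the same baseline is (m_j + τ + β_jB) − (m_j + β_jB) = τ at every visit. The baseline-by-visit slope cancels. With treatment-by-visit added, the difference becomes τ_j, which is six separate parameters.

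**What τ estimates.** With complete data, the generalised least squares estimate is w′d, where d holds the six visit differences and w = V⁻¹1 / (1′V⁻¹1). A random subject effect alone implies compound symmetry, so each weight is 1/6. With X the true Day 43 effect:

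| Assumed course of the effect | Sum of six visit effects ÷ 6 | Value reported for Day 43 |
|---|---|---|
| Constant | 6X/6 | X |
| Linear rise to a plateau at Day 15 | 5.5X/6 | 0.92X |
| Linear rise to a plateau at Day 22 | 5X/6 | 0.83X |
| Linear growth to Day 43 | 3.5X/6 | 0.58X |
| Linear fade from 2X to X | 9X/6 | 1.50X |

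**Dropout.** Assume 10–30% monotone dropout, equal by arm and spread evenly over the visits, and within-subject correlation r of 0.3–0.7. The last four rows become 0.88–0.91X, 0.78–0.82X, 0.52–0.57X and 1.52–1.58X. The constant case stays at X.

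**Other covariance structures.** For linear growth, AR(1) with correlation 0.8 also gives 0.58X. Heterogeneous AR(1) with correlation 0.8 gives 0.37X if the SD rises from 1 to 1.5, and 0.18X if it rises from 1 to 2.5.

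**Precision.** Under compound symmetry, the SE of the visit-specific Day 43 difference over that of the common difference is √(6/(1+5r)):

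- r = 0.3: √(6/2.5) = 1.549
- r = 0.5: √(6/3.5) = 1.309
- r = 0.7: √(6/4.5) = 1.155

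**Simulated check.** One data set had 350 subjects, compound symmetry of 0.6 and a linear effect reaching 0.5 at Day 43; site and stratum were left out.

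- As written: 0.233 (SE 0.094) at all six visits.
- With treatment-by-visit: −0.060, 0.088, 0.276, 0.333, 0.303 and 0.457. Their mean is 1.397/6 = 0.233. The SE at Day 43 is 0.112.
- ANCOVA fitted at Day 43 alone: 0.457 (SE 0.114).
- ANCOVA pooled over visits without a subject term: 0.233 (SE 0.046).

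The pooled ANCOVA's SE is too small by the factor 1/√(1+5r), which is 0.632, 0.535 and 0.471 at r = 0.3, 0.5 and 0.7.

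**The case against.** The strongest reply is that this is a damaged sentence and not a modelling decision. The term list has a doubled word and a plural that introduces a single interaction, the promised output shows the intent, and the efficacy models use near-identical wording with both interactions. The table shells are not in the visible documents and might settle it. This is a fair account of how the text arose, and the gap would probably surface at programming. It does not change what the visible text specifies, and nothing visible in 16.4 supplies the missing term.

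A second point is that the sentence on the random subject effect does not establish compound symmetry, since 15.1.3 uses the same sentence and then adds an unstructured covariance. That stands as a limit on the figures. The multipliers and interval widths above belong to one structure, and others can move the common value further from Day 43. No covariance structure makes the model visit-specific.

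Third, the stakes are modest. Protocol section 12.4, under Safety Analyses, calls between-group comparisons exploratory. That sentence directly follows one on chemistry results, and SAP 16.4 applies the label only to the ANCOVA, so its reach is arguable. By-visit descriptive summaries, markedly abnormal incidences and BMI shifts do not use this model.

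Finally, the ANCOVA is most naturally read as a separate fit at each time point, which would give a Day 43 comparison under LOCF. That is likely, but the wording "ANCOVA with LOCF model with effects for study visit" leaves it open: the visit effect has no role in a single-visit fit.

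**Conclusion.** The concern holds. The vital-sign MMRM in SAP 16.4 is wrong as written, because it cannot produce the Day 43 or per-visit differences that the same paragraph promises. That conclusion is algebraic and needs no assumption.

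The size does rest on assumptions. With a random subject effect and complete data, the reported Day 43 value ranges from 0.58 to 1.5 times the true one across the courses considered, and is right only for a constant effect. The documents do not say which course to expect.

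The correction should be made, but the consequence is confined to a between-group safety comparison. The primary and key secondary analyses are untouched.

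**What to change.** In SAP 16.4:

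- Add treatment-by-study visit to the MMRM, and take the per-visit and Day 43 differences from that contrast.
- State the covariance structure and degrees-of-freedom method, or cross-refer to 15.1.3 as 15.2 does.
- State that the LOCF ANCOVA is fitted separately at each time point, and remove study visit from its effects. Pooled over visits, it would give the same common value with an SE that is too small.

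The drafting cost is one model term, one covariance statement or cross-reference, and one sentence. The statistical cost is a wider Day 43 interval than the common-effect one: about 15–55% wider under compound symmetry with r from 0.7 down to 0.3 and complete data, or about 18–60% with 10% dropout. That is the price of estimating the quantity the section names.
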